9.2. Sample Size Determination

A sample size of 700 participants (350 in each treatment group) will provide roughly 80% power for the change from baseline to Week 52 in KCCQ-CSS using Wilcoxon rank sum test under the assumptions that the change from baseline to Week 52 in KCCQ-CSS follows normal distribution with mean of 5 and standard deviation of 19 in placebo and mean of 10 and standard deviation of 19 in tirzepatide group at a 2-sided alpha of 0.01 significance level. The expected events at the end of the study will provide roughly 80% power to demonstrate the superiority of tirzepatide MTD to placebo in occurrence of the composite endpoint of CV death and/or HF events at a 2-sided alpha of 0.04 significance level under the treatment effect estimate assumption of 0.5. The study power is calculated using nQuery Version 9.1.

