3.2. General Considerations

Statistical analysis of this study will be the responsibility of Eli Lilly and Company or its designee. Some analyses and summaries described in this analysis plan may not be conducted if not warranted by data (for example, too few events to justify conducting an analysis). Additional analyses of the data may be conducted as deemed appropriate.

Statistical treatment comparisons will be performed between tirzepatide MTD and placebo. Unless otherwise specified, all tests of treatment effects will be conducted at a 2-sided alpha level of 0.05, and all confidence intervals (CIs) will be given at a 2-sided 95% level. Efficacy will be assessed using the intent-to-treat (ITT) population. Baseline is defined as the last nonmissing observation collected prior to or at randomization for efficacy analyses. Safety will be assessed using safety population and the definition of baseline and postbaseline for safety analyses are specified in Table GPID.3.2.

Analysis Type	Baseline	Postbaseline
1.1) Treatment-Emergent	The baseline period is defined as	Starts after the first dose of study treatment
Adverse Events	the start of screening and ends	and ends at the end of follow-up. See
	prior to the first dose of study	Section 3.2 for the definition of a participant's
	treatment (typically at Week 0).	end of follow-up.
1.2) Treatment-Emergent	Baseline will include all scheduled	Postbaseline will be defined as measurements
Abnormal Labsa and	and unscheduled measurements	after Visit 2. All scheduled and unscheduled
Vital Signs	during the baseline period (Visit 1	measurements will be included.
	and Visit 2).	
Analysis Type	Baseline	Postbaseline
1.3) Change from Last	The last scheduled and	Postbaseline will be defined as above (1.2).
Baseline to Week xx and	unscheduled nonmissing	Only scheduled visits will be included. The ET
to Last Postbaseline for	assessment recorded during the	visits are considered scheduled visits.
Labsa and Vital Signs	baseline period defined above	
	(1.2).	

Table GPID.3.2. Baseline and Postbaseline Definitions for Safety Analyses

Abbreviations: ET = early termination.

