3.14. Safety Analyses

Unless specified otherwise, safety analyses will be conducted in the safety population (Table GPID.3.1). All events that occur between the first dose date of study drug and the end date of follow-up will be included in the safety analyses, regardless of the adherence to study drug.

The statistical assessment of homogeneity of the distribution of categorical safety responses between tirzepatide MTD and placebo will be conducted using Fisher's exact test, unless specified otherwise. Risk difference and its 95% CI will also be provided, where appropriate.

The mean change from baseline differences among treatments at all scheduled visits will be assessed via an MMRM analyses using REML. Unless specified otherwise, the MMRM analysis will contain measurements from planned visits up to 104 weeks, and the model will include treatment group, stratification factors, visit and treatment-by-visit interaction as fixed effects, and baseline value of the safety parameter as a covariate. To model the covariance structure within participants, the unstructured covariance matrix will be used. If this model fails to converge, the covariance structures specified in Section 3.13.1.4 will be tested in order until convergence has been met. If the data does not warrant the MMRM model, then an ANCOVA model will be conducted.

For selected safety parameters, a time-to-first-event analysis via the Cox-proportional hazards model may be conducted. Participants without the event will be censored at the end of follow-up.

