3.14.3.3. Exocrine Pancreas Safety

3.14.3.3.1. Pancreatic Enzyme

Observed pancreatic enzyme data (p-amylase and lipase) will be summarized by treatment and nominal visit.

The counts and percentages of participants with maximum postbaseline pancreatic enzyme value exceeding the following thresholds will be provided by baseline pancreatic enzyme value (\leq upper limit of normal [ULN], > ULN), and postbaseline: \leq 1 \times ULN, (>1 to \leq 3) \times ULN, (>5 to \leq 10) \times ULN, >10 \times ULN.

An MMRM analysis will be used to analyze each pancreatic enzyme with a log-transformed (postbaseline measure/baseline measure) response variable and treatment, nominal visit, and treatment-by-nominal visit interaction as fixed effects.

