3.14.5. Clinical Laboratory Evaluation

All safety laboratory data will be reported using the International System of Units and conventional units. Limits from the performing lab will be used to define low (L) and high (H). Descriptive summaries by treatment and by nominal visit will be provided for the baseline and postbaseline values as well as the change from baseline values.

For selected laboratory analyte measurements collected quantitatively, observed and change from baseline values for each visit may be displayed in plots for participants who have both a baseline and at least 1 postbaseline planned measurement. Baseline will be defined as the last nonmissing observation during the baseline period. Unplanned measurements will be excluded from plots.

A shift table will be provided, including unplanned measurements. The shift table will include the number and percentage of participants with a change from baseline to postbaseline of normal or high to low, and normal or low to high. The proportion of participants shifted will be compared between treatments using Fisher's exact test.

A listing of abnormal findings will be created for laboratory analyte measurements, including qualitative measures. The listing will include participant identification, treatment group, laboratory collection date, study day, analyte name, and analyte finding. Other variables may be added, as appropriate.

The MMRM model or ANCOVA (if the MMRM model is not applicable), as described in Section 3.14, will be used for the analysis for the continuous measurements for selected lab tests with or without log-transformed (postbaseline measure/baseline measure) response variables. For measures analyzed using log-transformed values, the results will be presented with the scale back-transforming to the original, related scale.

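### The pancreatic enzyme MMRM drops the baseline covariate and the stratification factors of the SAP's default safety model without giving a reason; restoring them is a free gain in precision

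*SAP*

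**What the plan says.** SAP 3.14.3.3.1 gives each pancreatic enzyme its own MMRM. The response is a "log-transformed (postbaseline measure/baseline measure) response variable", and the model terms are "treatment, nominal visit, and treatment-by-nominal visit interaction as fixed effects". Nothing else is listed.

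The default safety MMRM in SAP 3.14 is larger. It has "treatment group, stratification factors, visit and treatment-by-visit interaction as fixed effects", and in addition the "baseline value of the safety parameter as a covariate". The default can be overridden, since its description opens: "Unless specified otherwise, the MMRM analysis will contain measurements from planned visits up to 104 weeks".

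SAP 3.14.5 applies the Section 3.14 model to "selected lab tests with or without log-transformed (postbaseline measure/baseline measure) response variables". SAP 3.14.3.13 also uses the Section 3.14 MMRM for eGFR and for log-transformed UACR.

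**The concern.** A log ratio to baseline is a change score on the log scale. It subtracts the whole of log baseline, which is the best use of baseline only if log postbaseline rises one for one with log baseline. With regression to the mean the slope is below 1. The part of baseline that has been over-subtracted then stays in the error term, and a chance baseline difference between the arms carries through to the estimate, multiplied by (slope − 1).

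The SAP does not treat this response as a reason to drop baseline elsewhere: 3.14.5 keeps the default model for the same log ratio. The categorical enzyme table in 3.14.3.3.1 is itself split by baseline at or below ULN versus above ULN. The short list therefore looks unintended, or at least unexplained.

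At stake is the width of the intervals in the only model-based enzyme comparison that the pancreatic section specifies. Protocol 10.5.1.2 says the enzymes are measured to assess the effect of tirzepatide on their levels.

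**Working it through.** The plan states no figure for this model, so there is none to reproduce. The question is how much precision the baseline covariate adds.

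**Inputs**
- Response and terms: SAP 3.14.3.3.1. Comparator model: SAP 3.14.
- 350 participants per arm: Protocol 9.2.
- rho, the correlation of log baseline with log postbaseline: not in the documents. Assumed 0.5 to 0.9.
- k = SD of log postbaseline / SD of log baseline: not in the documents. Assumed 1, then varied.

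**Formulas** (baseline SD set to 1, slope b = rho × k)
- Listed model: variance ∝ 1 + k² − 2 × rho × k
- Baseline-adjusted model: variance ∝ k² × (1 − rho²)
- The first minus the second is (b − 1)². This cannot be negative and is zero only when b = 1. So in large samples the listed model is never more precise.

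This takes one slope for all visits. If slopes differ by visit, the same guarantee needs a baseline-by-visit term.

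**Equal SDs (k = 1).** The variances reduce to 2(1 − rho) and 1 − rho², with ratio adjusted/listed = (1 + rho)/2. The last column is 350 × (1 − ratio).

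| rho | Listed | Adjusted | Ratio | Variance lowered by | SE lowered by | Equivalent participants per arm |
|---|---|---|---|---|---|---|
| 0.5 | 1.00 | 0.75 | 0.75 | 25% | 13% | 88 |
| 0.7 | 0.60 | 0.51 | 0.85 | 15% | 8% | 53 |
| 0.8 | 0.40 | 0.36 | 0.90 | 10% | 5% | 35 |
| 0.9 | 0.20 | 0.19 | 0.95 | 5% | 3% | 18 |

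**Simulation check.** Four postbaseline visits, unstructured covariance, a common baseline slope, 350 per arm, complete data and 1,500 replicates. The SE ratio (listed/adjusted) at the last visit was 1.147, 1.083 and 1.018 for rho 0.5, 0.7 and 0.9. The formula sqrt(2/(1 + rho)) gives 1.155, 1.085 and 1.026. Mean estimates were close to the true value of zero under both models.

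**Unequal SDs**
- k = 1.25, rho = 0.8: b = 1. Listed 1 + 1.5625 − 2 = 0.5625; adjusted 1.5625 × 0.36 = 0.5625. No gain.
- k = 0.8, rho = 0.5: b = 0.4. Listed 1 + 0.64 − 0.8 = 0.84; adjusted 0.64 × 0.75 = 0.48. The listed model's SE is sqrt(0.84/0.48) = 1.323 times the adjusted one.

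The gain from the stratification factors was not calculated, because the documents give nothing on how strongly they predict enzyme levels.

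**The case against.** **The covariate may be implied.** Section 3.14 names baseline separately, as a covariate, while 3.14.3.3.1 lists only fixed effects. The sentence can be read as changing the fixed effects and keeping the covariate. That reading is possible. It does not bring back the stratification factors, which Section 3.14 lists among the fixed effects. If two programmers could fit two different models, the text needs the same sentence added.

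**SAP 3.14.5 may already cover the enzymes.** They are laboratory tests in Protocol Appendix 2, and the response is the same. But 3.14.5 speaks only of selected tests, and the pancreatic section has its own model. What 3.14.5 does show is that the log-ratio response is no reason to drop baseline.

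**The model matters little.** This stands. The pancreatitis AESI in SAP 3.14.3.3.2 rests on adjudication-confirmed events. The threshold table is already split by baseline. Protocol 10.5.1.2 says that serial enzyme values do little to predict acute pancreatitis in participants without symptoms. Safety comparisons carry no multiplicity adjustment (SAP 3.6).

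**Stronger readings that a reader might infer, and that the documents do not support:**
- *The model ignores baseline.* It does not. Baseline is the denominator of the response, and only the regression adjustment is missing.
- *The SAP contradicts itself.* The default allows overrides, so this is an unexplained departure.
- *The comparison is biased.* Randomisation keeps it unbiased on average under either model, and the ratio already removes part of any chance baseline difference.
- *A definite loss of precision is established.* Its size depends on a correlation and an SD ratio that the documents do not give, and it can be zero.

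**Conclusion.** The departure is real and no reason is given for it. As written, the p-amylase and lipase model leaves out the stratification factors and, on its plain reading, the baseline covariate. With one slope across visits it is generally less precise than the Section 3.14 model and never more precise in large samples.

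Assuming equal SDs and rho between 0.5 and 0.9, adding log baseline lowers the variance of the treatment difference by about 25% down to 5%, and the SE by about 13% down to 3%. If the true slope is 1, nothing is gained. Both rho and equal SDs are assumptions.

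No primary, key secondary or adjudicated pancreatitis result depends on this. It is a free improvement to a safety laboratory analysis.

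**What to change.** In SAP 3.14.3.3.1, state that the Section 3.14 MMRM applies to the log-ratio response, with log baseline enzyme value as a covariate and the stratification factors as fixed effects. Naming the log scale matters, because Section 3.14 says only that the baseline value is used.

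The cost is one sentence in the SAP and the added model terms. Baseline enzymes are already collected, and the stratification factors are already derived for the efficacy models (SAP 3.3). No new data, visits or participants are needed.

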3.14.3.3.2. Pancreatitis Events

Investigator-reported events will be searched using the "Acute pancreatitis" Standardized MedDRA Query (SMQ) (20000022, narrow scope) and a "Chronic pancreatitis" PT in the AE database, while adjudication-confirmed pancreatitis are found from adjudication forms.

A summary of adjudicated pancreatic events will be provided by treatment.

TE adjudication confirmed pancreatitis will be considered as AESI. A listing of participants with investigator-reported and adjudicated pancreatitis will be provided.

3.14.3.4. Gastrointestinal Adverse Events

3.14.3.4.1. Nausea, Diarrhea, Constipation, and Vomiting

Summaries and analyses for incidence and severity of nausea, diarrhea (including "diarrhea", "diarrhoea" and "frequent bowel movements"), constipation (including "constipation", "infrequent bowel movement" and "faeces hard"), and vomiting (including "vomiting" and "vomiting projectile"), and nausea, vomiting and diarrhea combined, will be provided by each treatment group.

Summary of the prevalence over time for nausea, diarrhea, constipation, and vomiting will also be presented. Time to onset of nausea, diarrhea, constipation, and vomiting will be plotted.

3.14.3.4.2. Severe Gastrointestinal Events

The PTs under the *Gastrointestinal (GI) disorders* SOC in MedDRA will be used to identify GI AEs, and only PTs with serious/severe TE cases will be considered as AESI.

The counts and percentages of participants with severe/serious TE GI events will be summarized by treatment.

3.14.3.5. Hepatobiliary Disorders

3.14.3.5.1. Hepatobiliary Events

The counts and percentages of participants with TE hepatic events will be summarized by treatment using the MedDRA PTs. The detailed search criteria can be found in Appendix 2, Section 5.2.

TE events related to acute gallbladder disease will also be summarized. The search criteria can be found in Appendix 2, Section 5.2.

Severe/serious TE hepatic events and severe/serious TE acute gallbladder disease will be considered as AESI and summarized separately.

In addition, counts and percentages of participants with acute gallbladder disease by weight change category will be provided by treatment.

3.14.3.5.2. Liver Enzymes

Common analyses for laboratory analyte measurements described in Section 3.14.1.5 are applicable for the liver enzyme related measurements. This section provides additional analyses for liver enzymes.

The counts and percentages of participants with the following elevations in hepatic laboratory tests at any time during the study will be summarized between treatment groups:

- The counts and percentages of participants with an alanine transaminase (ALT) measurement ≥1× ULN, ≥3× ULN, ≥5× ULN, ≥10× ULN, and ≥20× ULN will be summarized for all participants with a postbaseline value and for subsets based on the following baseline values:
 - o participants whose nonmissing maximum baseline value is $\leq 1 \times ULN$
 - o participants whose maximum baseline is >1× ULN, and
 - o participants whose baseline values are missing.
- The counts and percentages of participants with an aspartate aminotransferase (AST) measurement ≥1× ULN, ≥3× ULN, ≥5× ULN, ≥10× ULN, and ≥20 × ULN during the treatment period will be summarized for all participants with a postbaseline value and for subsets based on various baseline levels, as described above for ALT.
- The counts and percentages of participants with a total bilirubin (TBL) measurement $\ge 2 \times \text{ULN}$, $\ge 5 \times \text{ULN}$, and $\ge 8 \times \text{ULN}$ will be summarized for all participants with a postbaseline value and for the following subsets based on the baseline values:
 - o participants whose nonmissing maximum baseline value is $\leq 1 \times ULN$
 - \circ participants whose maximum baseline is >1 × ULN but <2 × ULN
 - o participants whose maximum baseline value is $\ge 2 \times$ ULN, and
 - o participants whose baseline values are missing.
- The counts and percentages of participants with a direct bilirubin (DBL) measurement ≥2× ULN AND ≥5× ULN will be summarized for all participants with a postbaseline value and for the same subsets as described for TBL.
- The counts and percentages of participants with a serum alkaline phosphatase (ALP) measurement ≥2× ULN and ≥3× ULN will be summarized for all participants with a postbaseline value and for the same subsets as described for TBL.
- The counts and percentages of participants with a gamma-glutamyltransferase (GGT) measurement ≥2× ULN will be summarized for all participants with a postbaseline value, if data available.

Maximum baseline will be the maximum nonmissing observation in the baseline period. The maximum value will be the maximum nonmissing value from the postbaseline period. Planned and unplanned measurements will be included.

Hepatocellular drug-induced liver injury screening plot will be created. The plot with maximum postbaseline transaminase (ALT or AST, whichever is higher, regardless of the time between the two maximum values) divided by ULN versus maximum postbaseline total bilirubin divided by ULN (y-axis) will be created that includes all participants from the safety populations. Each participant with at least 1 postbaseline ALT or AST and total bilirubin contributes 1 point to the plot. Dashed lines represent TBL and transaminase cut-offs of 2× ULN and 3× ULN, respectively. A potential Hy's law case is circled and is defined as having a maximum postbaseline TBL equal to or exceeding 2× ULN within 30 days after maximum postbaseline ALT or AST equal to or exceeding 3× ULN, without cholestasis (defined as ALP less than 2× ULN). The percentages of study participants falling in each of the three relevant quadrants of the plot (right upper, left upper, right lower) will be summarized in a table.

Cholestatic Drug-Induced Liver Injury Screening plot based on the maximum postbaseline TBL and ALP will be created, regardless of the time between the two maximum values. Dashed lines represent TBL and ALP cut-offs of 2× ULN and 3× ULN, respectively. A potential cholestatic liver injury case is circled and is defined as having a maximum postbaseline TBL equal to or exceeding 2× ULN within 30 days after maximum postbaseline ALP equal to or exceeding 3× ULN. The percentages of study participants falling in each of the three relevant quadrants of the plot (right upper, left upper, right lower) will be summarized in a table.

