8.2.5. Safety Monitoring

The sponsor will periodically review evolving aggregate safety data within the study by appropriate methods. The study team will review safety reports in a blinded fashion according to the schedule provided in the Trial-Level Safety Review Plan. The sponsor will also review SAEs within time frames mandated by company procedures. The Sponsor CRP will, as appropriate, consult with the functionally independent Global Patient Safety therapeutic area physician or clinical scientist.

8.2.5.1. Hepatic Safety Monitoring, Evaluation, and Criteria for Study Drug Interruption or Discontinuation

The following tables summarize actions to take based on abnormal hepatic laboratory or clinical changes.

Participants with normal or near-normal baseline (ALT, AST, or ALP <1.5x ULN)

If this laboratory value is observed	Then			
	Initiate or continue close hepatic monitoring	Initiate comprehensive evaluation	Interrupt or discontinue study drug	
ALT or AST ≥3x ULN	X			
ALP ≥2x ULN	X			
TBL ≥2x ULN ^b	X			
ALT or AST ≥5x ULN	X	X		
ALP ≥2.5x ULN	X	X		
ALT or AST ≥3x ULN with hepatic signs or symptoms ^a	X	X	X	
ALT or AST ≥5x ULN for more than 2 weeks	X	X	X	
ALT or AST ≥8x ULN	X	X	X	
ALT or AST $\ge 3x$ ULN and TBL $\ge 2x$ ULN ^b or INR ≥ 1.5	X	X	X	
ALP ≥3x ULN	X	X	X	
ALP ≥2.5x ULN and TBL ≥2x ULN ^b	X	X	X	
ALP \geq 2.5x ULN with hepatic signs or symptoms ^a	X	X	X	

^a Examples of hepatic signs or symptoms: severe fatigue, nausea, vomiting, right upper quadrant abdominal pain, fever, rash, and/or eosinophilia >5%.

^b In participants with Gilbert's syndrome, the threshold for TBL may be higher.

Participants with elevated baseline (ALT, AST, or ALP \geq 1.5x ULN)

If this laboratory value is observed	Then		
	Initiate or continue close hepatic monitoring	Initiate comprehensive evaluation	Interrupt or discontinue study drug
ALT or AST $\geq 2x$ baseline	X		
$ALP \ge 2x$ baseline	X		
TBL ≥2x ULN ^b	X		
ALT or AST ≥3x baseline or ≥250 U/L (whichever occurs first)	X	X	
$ALP \ge 2.5x$ baseline	X	X	
ALT or AST ≥2x baseline or ≥250 U/L (whichever occurs first) with hepatic signs or symptoms ^a	X	X	X
ALT or AST ≥3x baseline or ≥250 U/L (whichever occurs first) for more than 2 weeks	X	X	X
ALT or AST ≥4x baseline or ≥400 U/L (whichever occurs first)	X	X	X
ALT or AST $\ge 2x$ baseline or ≥ 250 U/L (whichever occurs first) and TBL $\ge 2x$ ULN ^b or INR ≥ 1.5	X	X	X
ALP ≥3x baseline	X	X	X
ALP ≥2.5x baseline and TBL ≥2x ULN ^b	X	X	X

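### The potential Hy's law flag uses only each participant's study-wide peak ALT/AST and peak bilirubin, so some concurrent rises are not circled

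*SAP*

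**What the plan says.** SAP 3.14.3.5.2 plans a hepatocellular screening plot with one point per participant: highest postbaseline ALT or AST against highest postbaseline TBL, each divided by ULN. The point is placed "regardless of the time between the two maximum values", and the percentage of participants in each of three quadrants, including the right upper one, is tabulated.

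On top of the plot sits a case definition. A circled point "is defined as having a maximum postbaseline TBL equal to or exceeding 2× ULN" occurring "within 30 days after maximum postbaseline ALT or AST equal to or exceeding" 3× ULN, with the added condition that ALP is below 2× ULN. No time point is given for the ALP condition.

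Just above the plot description, the same section fixes the key term: "The maximum value will be the maximum nonmissing value from the postbaseline period". Planned and unplanned measurements both count. This gives one value per analyte for the whole study, not one per episode.

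The cholestatic plot repeats the construction. Its circled case needs a maximum TBL of at least 2× ULN "within 30 days after maximum postbaseline ALP equal to or exceeding" 3× ULN.

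Protocol 8.2.5.1 works differently. Its action tables are headed "If this laboratory value is observed", so for participants with normal or near-normal baseline the combined criterion (ALT or AST at least 3× ULN with TBL at least 2× ULN) refers to observed values, with no reference to a study maximum.

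**The concern.** The circle exists to mark liver enzyme and bilirubin rises that occurred together. Built on two study-wide maxima, it depends on values that may have nothing to do with the joint rise. A later, higher ALT moves the ALT/AST maximum away from the episode, and the episode is then no longer examined. A later or earlier bilirubin peak can do the same.

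The maxima are taken over a long period: treatment lasts at least 52 weeks, and protocol 4.1 estimates up to 120 weeks of participation. Protocol 8.2.5.2 calls for testing 2 to 3 times weekly while an abnormality persists, and these unplanned values count, so the enzyme and bilirubin peaks of one episode can easily fall on different days. SAP 3.14 uses data to the end of follow-up whatever the adherence to study drug, so an ALT rise after stopping treatment can displace a joint rise that occurred on treatment.

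At stake is the reported number of potential Hy's law cases. The other liver tables in SAP 3.14.3.5.2 count each analyte separately, so outside the quadrant percentages no summary there looks at enzymes and bilirubin together.

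**Working it through.** The plan gives no figure on this point to reproduce. The check applies the stated rule to constructed laboratory series. These are assumptions for illustration, not trial data.

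**Inputs (SAP 3.14.3.5.2):** ALT/AST threshold 3× ULN; TBL threshold 2× ULN; window 30 days after; ALP below 2× ULN; maximum taken over the whole postbaseline period. ALP is set at 1× ULN throughout, so the missing time point for ALP plays no part.

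**Rules.** Let dA be the day of the overall highest ALT/AST and dB the day of the overall highest TBL.

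- Literal: max ALT/AST ≥ 3, max TBL ≥ 2, and 0 ≤ dB − dA ≤ 30.
- Lenient: max ALT/AST ≥ 3, and the highest TBL between dA and dA + 30 is ≥ 2.
- Any-pair: some ALT/AST ≥ 3 on day i and some TBL ≥ 2 on day j, with 0 ≤ j − i ≤ 30.

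**Results** (values are ALT / TBL in multiples of ULN):

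| Series | dB − dA | Highest TBL in the 30 days from dA | Literal | Lenient | Any-pair |
|---|---|---|---|---|---|
| 1. Day 84: 4 / 2.5 only | 84 − 84 = 0 | 2.5 | circled | circled | circled |
| 2. Day 84: 4 / 2.5; day 364: 6 / 0.9 | 84 − 364 = −280 | 0.9 | no | no | circled |
| 3. Day 84: 4 / 2.5; day 364: 1 / 3 | 364 − 84 = 280 | 2.5 | no | circled | circled |
| 4. Day 84: 4 / 2.5; day 91: 5 / 2.2 | 84 − 91 = −7 | 2.2 | no | circled | circled |
| 5. Day 84: 4 / 0.8; day 364: 1 / 2.5 (unrelated) | 364 − 84 = 280 | 0.8 | no | no | no |

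Series 1 to 4 contain a concurrent rise. The literal rule circles 1 of 4, the lenient reading 3 of 4, the any-pair rule 4 of 4. The any-pair rule correctly leaves out series 5, where the rises are 280 days apart.

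Two points follow.

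- Series 2 is missed under both readings, so that gap does not depend on how the sentence is read. Series 3 and 4 are missed only under the literal reading, which the section's own definition of the maximum supports.
- All five series have max ALT ≥ 3 and max TBL ≥ 2, so all five lie in the right upper quadrant. Series 2 (a true joint rise) and series 5 (two unrelated rises) then look alike: same quadrant, neither circled.

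The cholestatic flag follows by replacing ALT/AST with ALP in the literal and lenient rules. The same failures arise.

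**The case against.** The strongest reply is that nobody drops out of the analysis. The plot ignores timing, so anyone with ALT/AST at least 3× ULN and TBL at least 2× ULN at any time is in the right upper quadrant and in its percentage. That group contains every case the any-pair rule could find. This stands, and it limits the point to the circle.

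Other routes also lead to the same participant. Protocol 8.2.5.1 acts on observed values and sets out extra hepatic data collection. SAP 3.14.5 lists abnormal laboratory findings with collection date and study day. SAP 3.14.3.5.1 summarises hepatic adverse events. SAP 3.14.2 requires narratives for serious adverse events and for permanent discontinuation due to adverse events. A careful reader could reconstruct the timing. That stands too, but none of these routes restores the stated flag, and being in the quadrant does not by itself trigger a narrative.

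Series 2 can be challenged on conduct. In a participant with normal or near-normal baseline, the day-84 values call for interruption or discontinuation under protocol 8.2.5.1, and 8.2.5.4 permits resumption only under stated conditions, including an identified cause other than study drug. So the later ALT peak would probably arise off drug, or after the first episode had been explained. This makes the pattern less likely to go unnoticed. It does not cure the rule: if the drug was stopped and never resumed, the first episode is the one of interest, and the off-drug peak removes its flag.

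The SAP version history says the liver categorisation was aligned with a sponsor hepatic analyses plan that is not available here. That plan may specify case-level timing; the SAP as written does not.

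**Conclusion.** The point holds as a modest gap in an analysis definition. The potential Hy's law flag can miss a concurrent rise under either reading when ALT/AST later peaks higher with normal bilirubin. Under the literal reading it also misses one when TBL peaks before, or more than 30 days after, the ALT/AST peak. The cholestatic flag shares the gap.

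Its size in this trial cannot be computed, because neither document gives a rate of such events. The 1-of-4 and 3-of-4 results describe constructed series and are not expected proportions.

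A reader might infer more than the documents support:

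- *That cases vanish and liver risk is understated.* The quadrant percentage still includes them; only the number of circled points can be too low.
- *That participants are less well protected.* Monitoring and drug decisions follow the protocol, not this flag.
- *That SAP and protocol contradict each other.* A clinical action trigger and a plot annotation serve different purposes and may differ.
- *That repeated liver episodes are expected here, or that a single case would settle a safety review.* Neither document says so. Protocol 8.2.5.2 names heart failure among recent illnesses to ask about when liver tests are abnormal, but gives no frequency. A circle marks a potential case, not a confirmed one.

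**What to change.** This changes the analysis only; thresholds and clinical actions stay as they are.

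- Keep the participant maxima for the plot axes and the quadrant table.
- Define a potential Hy's law case as any postbaseline TBL at least 2× ULN within 30 days after, or on the same day as, any postbaseline ALT or AST at least 3× ULN, with ALP below 2× ULN assessed at that ALT/AST elevation.
- Define the cholestatic case with the same pairing: any postbaseline TBL at least 2× ULN within 30 days after, or on the same day as, any postbaseline ALP at least 3× ULN.

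The cost is a few lines of SAP text, a small programming change using laboratory data already collected, and possibly a few more circled points to review.
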